9.2.1. Inclusion Criteria

1. Patients diagnosed with a gastroenteropancreatic neuroendocrine tumor by histopathological study.
2. Legally capable patients ≥ 18 and ≤ 80 years of age.
3. Patients who have signed the informed consent for this study as specified in section 10.3.
4. Patients in active treatment: active treatment is considered to be those patients in an advanced stage and in any type of medical treatment (somatostatin analogues, molecular therapies, chemotherapy, radionuclides...), or locoregional therapies.

Note: Decision was taken to treat the patient with an specific treatment prior and independently of patient inclusion in this non interventional study.

9.2.2. Exclusion Criteria

1. Patients <18 or > 80 years of age.
2. Female patients that are currently pregnant.
3. Patients with a gastroenteropancreatic neuroendocrine tumor lacking an histopathological diagnosis.
4. Patients in palliative treatment or terminal stage.
5. Patients who have not signed the informed consent or any situation or condition that compromises the giving of patient voluntary informed consent.

9.3. Study Size

The sample size calculation is based on the expected prevalence of malnutrition

among NET patients in Spain, which was inferred from previous studies [1-7]. We expect to include a total number of 400 patients with GEP NETs.

Assuming an estimated prevalence of malnutrition of around 30% (according to previous studies) and establishing as a precision criterion for its determination a length of the confidence interval (CI) of +/- 5 percentage units, it has been estimated by Monte Carlo simulation that the sample size required to reach the 5% CI would be 300 patients. However, taking into account the uncertainty in the initial assumption, it has been decided to increase the precision to a confidence interval length of +/- 3 percentage units, resulting in a required sample size of 400 patients. This size of 400 patients will also allow the secondary endpoints to be addressed with sufficient statistical power to obtain conclusive results or generate new hypotheses of interest to be tested in future studies.

[figure not shown]

Figure 2. Calculation of sample size for a 5% CI on malnutrition prevalence.

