9.8. Data analysis

The study will be analyzed descriptively, using descriptive epidemiological methods as detailed below. All results, including p-values and confidence intervals, are to be interpreted descriptively only.

- The analyses will be performed to the total population included fulfilling all selection criteria.

Additional subgroup analyses may be performed to fulfill secondary objectives (depending on the finally observed number of patients in such subgroups), including but not limited to: Tumor type, stage, grade and functionality, treatment type or survival.

The data will be summarized using the mean (standard deviation) and the median (1st and 3rd quartiles) in the case of continuous variables and using relative and absolute frequencies in the case of categorical variables. The prevalence together with its corresponding 95% confidence interval will be estimated by fitting a binomial model. The associations between the nutritional status and the quality of life of the patients, the stage of the disease and the tumor grade will be contrasted using ordinal regression models. Survival will be analyzed using cox regression models or parametric survival models according to the assumptions that meet the data. All analyzes will be performed using R software (version 4.03 or higher).

The final analysis will be performed within 6 months after the inclusion of the last patient. The final data interpretation and presentation in reports, scientific publications and/or congresses will be done within 12 months after the final analysis. The final report will be presented to the competent authorities 12 months after the end of study.

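### 400 patients do not give the stated ±3-point precision: at 30% prevalence the 95% CI is about ±4.5 points, and ±3 needs about 897 patients

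*Combined protocol and SAP*

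**What the plan says.** Section 9.3 (Study Size) builds the sample size on the precision of one prevalence estimate. The section 4.2 synopsis carries the same text.

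- Starting assumption: "Assuming an estimated prevalence of malnutrition of around 30% (according to previous studies").
- Initial criterion: "establishing as a precision criterion for its determination a length of the confidence interval (CI) of +/- 5 percentage units".
- Result for that criterion: "it has been estimated by Monte Carlo simulation that the sample size required to reach the 5% CI would be 300 patients".
- Final criterion, adopted because the starting assumption is uncertain: "a confidence interval length of +/- 3 percentage units, resulting in a required sample size of 400 patients".
- Planned size: "We expect to include a total number of 400 patients with GEP NETs".

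Section 9.3 does not give the confidence level. It comes from section 9.8 and the synopsis: "The prevalence together with its corresponding 95% confidence interval will be estimated by fitting a binomial model".

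The same paragraph of section 9.3 adds that 400 patients give enough power for the secondary endpoints to yield conclusive results or new hypotheses. No power calculation is shown. Section 9.8 states: "All results, including p-values and confidence intervals, are to be interpreted descriptively only".

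**The concern.** Cutting the half-width from 5 to 3 points is a large gain in precision, yet the plan obtains it by adding only a third more patients (300 to 400). Half-width shrinks with the square root of the sample size, so this cannot be right.

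The primary objective is to describe a prevalence, and interval width is the only quantitative argument offered for 400 patients. If the ±3 figure is wrong, an ethics committee or reader expects roughly 27% to 33% around an estimate of 30%, while the study would report roughly 25.5% to 34.5%. The move from ±5 to ±3 is also presented as a deliberate safeguard against an uncertain prevalence, and at the size claimed that safeguard does not exist.

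**Working it through.** **Inputs**

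| Input | Value | Source |
|---|---|---|
| Prevalence p | 0.30 | 9.3 and 4.2 |
| Confidence level | 95% two-sided, z = 1.96 | 9.8 and 4.2 |
| Half-width h, initial and final | 0.05 and 0.03 | 9.3 and 4.2 |
| Stated n, initial and final | 300 and 400 | 9.3 and 4.2 |

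Formulas for a single binomial proportion: n = z² p(1−p) / h², and h = z √(p(1−p)/n). Here p(1−p) = 0.30 × 0.70 = 0.21.

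**Step 1. The plan's ±5 figure**

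- n = 1.96² × 0.21 / 0.05² = 322.7, so 323 against the stated 300.
- At n = 300: h = 1.96 × √(0.21/300) = 5.19 points.
- If the simulation asked how often the estimate falls within 5 points of the true 30%, the exact binomial answer at n = 300 (75 to 105 cases) is 0.949. That rounds to 95%, so 300 is a plausible simulation result.

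**Step 2. The plan's ±3 figure**

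- n = 1.96² × 0.21 / 0.03² = 896.3, so 897 against the stated 400.
- At n = 400: h = 1.96 × √(0.21/400) = 4.49 points. The ratio 4.49/3 is 1.50.
- The exact (Clopper-Pearson) interval for 120/400 is 25.5% to 34.8%, a half-width of 4.60 points.
- On the simulation reading of step 1, the probability of falling within 3 points at n = 400 (108 to 132 cases) is 0.83, not 0.95. At n = 897 it is 0.951.

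**Step 3. Consistency of the two pairs, without using p or the confidence level**

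With both held fixed, n is proportional to 1/h².

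- From ±5 to ±3: 300 × (5/3)² = 300 × 2.78 = 833, not 400.
- From 300 to 400: 5 × √(300/400) = ±4.3, not ±3.

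**Step 4. Does another reading give 400 for ±3?**

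| Reading | n for ±3 |
|---|---|
| Wilson interval | 894 |
| Clopper-Pearson interval | 927 |
| Continuity-corrected | 930 |
| Prevalence 25% | 801 |
| Prevalence 35% | 972 |
| 90% CI, or one-sided 95% | 632 |
| 80% CI | 384 (but then ±5 needs only 138) |
| Finite-population correction with the registry of about 3,000 (section 7; not invoked by the plan) | 691 |

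Working backwards, ±3 with 400 at p = 0.30 means z = 0.03/√(0.21/400) = 1.309, an 81% interval. Keeping 95%, it needs a prevalence of about 10.5%.

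**Step 5. What 400 delivers at 95% over a range of prevalence**

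| Prevalence | Half-width at n = 400 |
|---|---|
| 25% | ±4.24 |
| 30% | ±4.49 |
| 35% | ±4.67 |
| 50% (worst case) | ±4.90 |

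**The case against.** The arithmetic on ±3 has no good answer, but several points in the plan's favour deserve weight.

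- **The 300 figure.** The plan cites simulation, not a closed formula, for "the sample size required to reach the 5% CI would be 300 patients". The 0.949 in step 1 supports it, and at 25% prevalence ±5 needs only 289. This stands: 300 is a near miss, not the error. The formula half-width at 300 patients and 30% is still ±5.2.
- **The confidence level.** Section 9.3 does not state 95%, so taking it from section 9.8 is an inference. It is a natural one, and the scaling argument in step 3 does not need it.
- **The missing figure.** Figure 2 is not available to us. Its caption concerns the 5% criterion only, so it is not expected to support ±3.
- **400 is still a sensible size.** It meets the initial ±5 criterion at every prevalence (worst case ±4.9), so it does protect against an uncertain starting assumption. This stands, and is why the sample size need not change.
- **Little hangs on ±3 later.** No test or decision rule uses it, and the final report will show the actual interval. That limits the harm to the results, but not to those who approve or judge the design on the stated figure.
- **The power sentence is hedged.** It offers conclusive results or new hypotheses, so its conflict with the descriptive-only rule is partial. The unsupported power claim remains.

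**Conclusion.** The concern holds. On the plan's own inputs (30% prevalence, 95% interval, single binomial proportion), 400 patients give ±4.5 points, about 50% wider than the stated ±3. The ±3 target needs about 897 patients, more than twice the planned number. The two stated pairs are incompatible with each other at any single prevalence and confidence level.

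The figures assume independent patients and complete assessments. The documents give no intraclass correlation for the 16 hospitals, so no clustering effect is quantified here. Positive correlation within hospitals, or missing assessments, could widen the interval further.

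This must be corrected, because it is a demonstrable error in the one figure on which the primary sample size rests. It does not make the study unworkable.

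**What to change.** Keep 400 patients and make these wording changes in both section 4.2 and section 9.3:

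1. Delete the ±3-point claim and its link to 400.
2. Replace it with a statement such as: with 400 patients and a prevalence of 30%, the expected half-width of the 95% CI is about 4.5 percentage points (about 5.2 with 300 patients). State the 95% level in the sample size section itself.
3. The wish to allow for an uncertain prevalence can stay, with a true reason: 400 patients keep the half-width below 5 points at any prevalence (at most ±4.9).
4. Replace the claim of sufficient power for conclusive secondary results with a statement that the secondary analyses are descriptive and may generate hypotheses, in line with section 9.8.

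The cost is a wording amendment and a less favourable stated precision, with no extra patients and no change to the analysis. If the sponsor does require ±3 points, the alternative is about 897 patients, which is a different study in size and duration.

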9.4. Sampling and recruitment method

Patients will be consecutively included, in compliance with the previously established inclusion criteria. Recruitment at that centre will stop until further notice (e.g. if there is a need for recruitment).

According to the definition of study population and disease established in this scientific report, patients will be selected from cases histologically diagnosed with GEP NETs.

To prevent two or more reporting physicians from logging the same case, a coordinator, who controls the cases included in his or her centre, is appointed in health centres with several reporting physicians, and preventive measures are implemented in the tool controlling duplications in variables (such as age, gender, centre or diagnosis date).

9.4.1. Case Definition

A 'case' is defined as any patient, diagnosed, treated, or followed in the different health centres where reporting physicians authorised by the sponsor, who meets the inclusion criteria.

Healthcare will be provided following the applicable clinical criteria, in the context of usual clinical practice, regardless of patient inclusion in the study and following the best criteria of the specialists responsible for the patients.

9.5. Endpoints

- Demographic characteristics: Age and ECOG at inclusion, sex, complete physical examination (including blood pressure and heart rate), enolic and smoking habits, other cancer history.
- NET diagnosis: date of initial diagnose, age at diagnose.
- NET at baseline: location of primary tumor, histological grade, TNM grade, Ki-67, mitotic index, metastatic locations, functional status of the tumor.
- NET treatment:
 - a. Prior treatments: systemic therapies for NET (type, start and end date, best response, progression date), locoregional therapies (type, start and end date, best response, progression date), surgery (dates, outcome) and radiotherapy (type, dose, start and end date).
 - b. Current treatments (at baseline): systemic therapies for NET (type, start date, best response), locoregional therapies (type, start date, best response) and radiotherapy (type, dose, start date).
 - c. Hospitalizations (at baseline): cause, start and end date.
- Target nutritional history: regular weight, loss of weight (start date, duration), weekly food intake (calculation of mean daily caloric intake, mean protein intake, (animal and vegetal), mean carbohydrates intake (simple or complex), mean fat intake (saturate, monounsaturated, polyunsaturated, n-3 and n-6), and mean fiber intake (soluble and insoluble). The PREDIMED score test will be used (appendix 2). Calculation of caloric-protein nutritional requirements, according to ESPEN guidelines. Need for supplementation, if necessary, type of oral nutritional supplement (ONS) used, volume administered (ml / day), type of administration regimen (continuous or discontinuous). Number of intakes per day and volume of intakes and existence of intolerance related to enteral nutrition (EN): Diarrhea, constipation, bloating, nausea, vomiting, regurgitation, fever, ...).
- Nutritional screening test: NRS test (nutritional risk screening) (appendix 3) and SGA test (subjective global assessment) (appendix 4). The GLIM criteria for diagnosis and stratification of malnutrition will be applied.

- Quality of life (QoL) test: EORTC QLQ-C30 (European Organisation for Research and Treatment of Cancer Quality of Life Questionnaire)(appendix 5) and the NET specific questionnaire (GI.NET21)(appendix 6).
- Anthropometry: height, weight at baseline, BMI, triceps fold, brachial circumference, abdominal circumference, calf circumference.
- Bioelectrical impedance: resistance and reactance recording, phase angle calculation, total body water, fat compartment, muscle compartment. Obtaining the basal metabolic rate.
- Dynamometry: measurement of muscle strength.
- Blood biochemical analysis: glucose, A1c, peptide c, complete lipid profile (total cholesterol, HDL, LDL and triglycerides), renal function, blood count, hemostasis, total proteins, albumin, prealbumin, transferrin, iron metabolism, calcium-phosphorus metabolism, magnesium, vitamin B12 , folic acid, vitamin A, D and E, retinol binding protein.

Note: If there is a previous blood biochemistry analysis performed within 15 days prior to patient inclusion and containing all the items required and listed above, this test may be used for the patient in order to avoid further interventions.

- Pregnancy test at screening (only when applicable, WOCBP).

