8.2. Secondary Objectives

- Describe the nutritional status of NET patients by using clinical malnutrition scores, anthropometry, bioimpedanciometry, and analytical parameters.
- Describe the nutritional status of NET patients according to the type of NET.
- Study the association between the nutritional status and the quality of life of the patients.
- Study the association between the nutritional status and the stage of the disease and tumor grade.
- Study the association between the nutritional status and the treatments received by the patient.

- Study the association between the nutritional status and the hormonal functionality of the tumor.
- Study the association between nutritional status and survival of NET patients.
- Describe specific deficiencies or deficiencies of vitamins or trace elements in these patients and study if there is a correlation of these with the treatments or tumor types.

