9.5.1. Timing for documenting endpoints

Once the patient accepts to participate in the study by signing the informed consent, information on the clinical history will be reviewed to gather the necessary data and to complete the electronic forms of the study designed for this purpose. The patient will have a visit with a nutritionist, specialized nurse or specialist doctor (variable depending on the characteristics of the center) within the next 10 days after ICF signature to perform the test and fulfill the questionnaires specified below:

- Complete physical examination
- PREDIMED and nutritional history
- Nutritional screening test (NRS, SGA)
- Quality of life test (EORTC QLQ-C30, GI.NET-21)
- Anthropometry
- Bioelectrical impedance
- Dynamometry
- Blood biochemical analysis and pregnancy test (if applicable, see section 9.5)

After the gathering of all the information specified in the eCRF, data from clinical history, test and questionnaires performed, the qualified site staff will fill all the information on the eCRF during a stipulated period of 30 days after the patients visit.

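### A reused blood panel can be up to 25 days older than the nutrition visit and can predate the current treatment, and no rule keeps such samples out of the vitamin-by-treatment analysis

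*Combined protocol and SAP*

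**What the plan says.** Section 9.5 lists the blood tests, including vitamins A, D, E and B12, folic acid, prealbumin and retinol binding protein. It accepts an earlier panel on this condition: "If there is a previous blood biochemistry analysis performed within 15 days prior to patient inclusion and containing all the items required". Apart from the 15 days, the only condition is completeness: "containing all the items required and listed above, this test may be used for the patient in order to avoid further interventions".

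Section 9.5.1 places the screening scores, questionnaires, anthropometry, impedance, dynamometry and bloods at one visit, "within the next 10 days after ICF signature to perform the test".

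Inclusion criterion 4 in section 9.2.1 reads "Patients in active treatment: active treatment is considered to be those patients in an advanced stage and in any type of medical treatment". Its note adds "Decision was taken to treat the patient with an specific treatment prior and independently of patient inclusion". Neither sets a minimum time on treatment.

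Section 8.2 plans to describe vitamin and trace element deficiencies and to "study if there is a correlation of these with the treatments or tumor types". It also describes nutritional status through scores and laboratory values together.

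Section 9.5 collects start dates for current systemic, locoregional and radiotherapy treatments. It does not name the blood sampling date as a variable. Section 9.8 has no rule that compares a sample date with a treatment start.

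**The concern.** The two windows run in opposite directions from the same day. The reuse window runs back from inclusion, while the visit window runs forward from consent. Nothing limits the distance between the sample and the assessments it is described alongside, although section 9.1 calls the design cross-sectional. Several instruments have short recall: the intake item of the NRS form (Appendix 3) covers the preceding week, most QLQ-C30 items (Appendix 5) the past week, and the symptom item of the scored SGA form (Appendix 4) the last two weeks. A panel at the far end of the allowed gap falls outside all three periods.

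The second issue concerns exposure. A vitamin level measured before a treatment began cannot reflect that treatment. If such a sample is grouped by current treatment, it pulls the group towards its pre-treatment level. Recent starters make up a larger part of a short treatment line than of a long one, so any dilution would differ between the treatments compared.

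**Working it through.** The documents state no figure for the gap or for the affected share, so there is no plan figure to reproduce.

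**Maximum gap.** Inputs: 15 days back (section 9.5) and 10 days forward (section 9.5.1), with inclusion taken as the day of consent, day 0. Gap = 15 + 10 = 25 days. If the visit is on day 0 the maximum is 15 days.

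**When a reused panel predates the current treatment.** Three things must coincide:
- the current treatment began within the 15 days before inclusion;
- the site reuses a complete panel;
- that panel was drawn before the treatment started.

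**Affected share.** The documents supply none of these probabilities. The assumptions are:
- inclusion falls evenly over a line lasting T days, so P(started within 15 days) = 15/T;
- a proportion q of patients reuse a panel, with q from 0.10 to 0.50, regardless of how recently treatment began;
- draw and start both fall evenly over the 15 days, so half of the draws precede the start.

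Share = (15/T) × 0.5 × q.

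| T (days) | 15/T | share at q = 0.10 | share at q = 0.50 |
|---|---|---|---|
| 60 | 25.0% | 1.25% | 6.25% |
| 180 | 8.3% | 0.42% | 2.1% |
| 365 | 4.1% | 0.21% | 1.0% |
| 1095 | 1.4% | 0.07% | 0.34% |

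The ratio between a 6-month and a 3-year line is 1095/180 = 6.1, whatever q is.

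**In patients.** If all 400 were on 6-month lines, 400 × 0.0042 to 400 × 0.021 gives about 2 to 8 patients. If all were on 3-year lines, 400 × 0.0007 to 400 × 0.0034 gives about 0.3 to 1.4.

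**Sensitivity.** If every reused panel in a recent starter preceded the start, the factor 0.5 becomes 1 and the shares double: 0.8% to 4.2% at 180 days and 0.1% to 0.7% at 1095 days.

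**Effect on a comparison.** If a share f of a treatment group carries pre-start samples, a true treatment difference is observed at (1 − f) of its size. At f = 2.1% that is 0.979, a loss of about 2%.

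**The case against.** The strongest reply is that this is a deliberate choice with little effect. Reuse spares patients a further blood draw, which suits a non-interventional study. A panel qualifies only if it holds every listed item, including vitamins A and E and retinol binding protein, and that limits reuse. The 25 days is a worst case. Section 10.6 already lists non-standardised time-points as a limitation, and section 9.8 treats all results as descriptive. The eCRF is a stand-alone document and may already hold the sample date. A sample drawn one day after the start says hardly more about a treatment than one drawn the day before.

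Most of this stands, and it limits the size of the problem. It does not supply a rule for samples that predate the treatment, and the general limitation in section 10.6 does not say how they will be handled.

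Some stronger readings are not supported:
- A reader might infer that the plan does credit pre-treatment levels to the current treatment. It does not say so. Section 9.8 names no model for this objective, and section 8.2 refers to treatments in general while section 9.5 collects both prior and current ones. The plan allows the error but does not prescribe it.
- A reader might take 15/T (8.3% or 1.4%) as the affected share. That is the share of recent starters. Reuse and a draw before the start are also needed.
- A reader might extend the point to panels drawn before a hospital admission. No objective in section 8.2 compares patients by admission.
- A reader might suppose that complete panels were ordered because deficiency was suspected, or try to put a figure on how far an older sample weakens the link between laboratory values and nutritional status. The documents give no basis for either.

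**Conclusion.** The point holds as a small, cheaply corrected gap in the timing rules. The 25-day maximum follows directly from the two stated windows, taking inclusion as the day of consent. That a reused panel can predate the current treatment follows from the absence of any condition against it.

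The share of patients affected cannot be derived from the documents. Under the stated assumptions it is about 0.4% to 2% for a 6-month line and under 0.4% for a 3-year line. It is higher for shorter lines, so it is uneven across treatments. Nothing here threatens the study's conclusions as a whole. The NRS form uses no laboratory value. Among the appended screening forms, only the albumin and prealbumin items of the SGA form in Appendix 4 offer a route to the primary prevalence.

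Those items raise a related inconsistency. The form labels albumin as a value from before cancer treatment and prealbumin as one from after it, whereas section 9.5 asks for a single panel with no timing relative to treatment. One panel generally cannot supply both values as labelled, so the two places need to be reconciled.

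**What to change.** 1. In the section 9.5 note, count the 15 days back from the nutritional assessment visit instead of from inclusion. The maximum gap falls from 25 to 15 days.
2. Capture the blood sample date in the eCRF, or confirm that it is already there.
3. In section 9.8, state that analyses relating vitamins or proteins to current treatment exclude samples dated before the recorded start of that treatment. At the least, run a sensitivity analysis without them and report how many there are.
4. Do not bar all pre-treatment panels, because the SGA form asks for a pre-treatment albumin. Reconcile the note with Appendix 4 by stating which sample date each of the two protein items refers to.

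The cost is one reworded sentence, one date field, one analysis filter and a clarification to the form. The downside is that a few more patients have the blood draw already scheduled for the visit instead of reusing an older result. The sample date is best captured while data are being collected, although laboratory reports are source data (section 9.6) and it could be recovered from them later with more work.
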